## **Introduction**

Periodontal disease (PD) is a prevalent and preventable oral health issue that has a significant impact on adolescents globally. In Palestine, particularly among school-aged youth, the rates of gingivitis and calculus are concerningly high, compounded by limited access to preventive oral health initiatives. Adolescents are particularly susceptible to PD due to various behavioural, hormonal, and dietary influences. Implementing school-based oral health education is a cost-effective and scalable approach to enhance students' knowledge, attitudes, and practices regarding oral hygiene.

## **Primary Aim of this study**

To evaluate the effectiveness of a two-month interactive school-based oral health education program in reducing periodontal disease among 15-year-old students in Nablus City, Palestine, using clinical indices such as the Community Periodontal Index for Treatment Needs (CPITN) and the Simplified Oral Hygiene Index (S-OHI).

## **Secondary Aims**

To assess the effect of the intervention on students' oral hygiene practices, including brushing frequency, technique, and duration.

To evaluate changes in dietary habits following the intervention, particularly regarding breakfast consumption and intake of nutritious foods.

To examine changes in smoking behaviours, including cigarette and waterpipe use, among students exposed to the educational sessions.

## **Study design**

A pre-test/post-test experimental design was utilised.

The study adopted an interactive educational approach to teach oral health self-care. This method actively engaged participants through two-way communication, practical demonstrations, and hands-on activities.

## Sample techniques and process

This study employed a multistage sampling technique to ensure a representative sample of schools and students from Nablus City. Schools and students were selected using a stratified simple random sampling method. This randomness in selection helped create comparable groups, thereby reducing potential biases and confounding factors that could influence the relationship between the intervention and outcomes.

**Table 1. Geographical Distribution and Proportional Sample Allocation of Schools in Nablus**

Area	Total Schools	Proportion of Total	Sample Size (Proportional)
East	27	41.5%	6
Nablus			
Central	25	38.5%	6
Nablus			
West	13	20.0%	3
Nablus			
Total	65	100%	15

To ensure proportional representation, schools were evenly selected from three geographical areas of Nablus (East, Central, and West), corresponding to the number of schools in each area (Table 1). The Epi Info program was used to calculate the sample size based on schools with 9th-grade classes (East = 27, Central = 25, West = 13). A total of 15 schools were selected: 6 from East Nablus, 6 from Central Nablus, and 3 from West Nablus. The final sample included 10 governmental schools and 5 private schools, ensuring proportional distribution across the city.

Schools were eligible for inclusion if they had 9th-grade classes, were feasible for participation in the study and data collection and implemented an appropriate consent

process for students and their parents. According to the educational directorate's records for 2024, Nablus City had 2832 9th-grade students in governmental schools (males = 1360, females = 1472) and 737 students in private schools (males = 434, females = 303).

The G\*Power program was used to estimate the required sample size for the study, following the guidelines of Kang (2015, 2020). The effect size was set at  $dz = 0.5$ , with an alpha error probability ( $\alpha$ ) of 0.05 and a study power of 90% ( $1 - \beta$ ).

Based on these calculations, 536 students from intervention schools and 410 students from control schools were required to obtain accurate and meaningful data.

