### **Data Collection Processes**

The Al-Quds Committee for Ethical Considerations approved this study (REF.13/24). Consent forms were distributed to students, and their approval was sought before data collection began.

The researcher trained five dentists to conduct interviews and dental examinations, ensuring the data collection process was standardised and calibrated. Training sessions for the data collectors were held every 15 days throughout the research period to maintain consistency and accuracy in data collection.

During the baseline phase, all participants were provided with a comprehensive explanation of the study. Baseline data were collected in March 2024. The selected participants were randomly divided into intervention and control groups, ensuring that both groups were matched by age and gender. The control group received one oral educational session, while the intervention group participated in six sessions. The educational sessions were held every 10 days over two months.

After two months of interactive education, participants were re-examined and interviewed. Follow-up data were collected in the same schools using the same dental examination measures and questionnaires used during the baseline phase.

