Statistical Analysis Plan (SAP)

Official Title: Effectiveness of an Interactive School-Based Oral Health Education Program in Reducing Periodontal Disease Among Palestinian Adolescents: A Double-Blind Intervention Study

NCT Number:

Document Date: March 1, 2024

Sponsor: Al-Quds University

Overview

This Statistical Analysis Plan outlines the statistical methods and procedures used to analyse data for the intervention study assessing the effect of a school-based oral health education program on periodontal conditions and related behaviours among 9th-grade students in Nablus City, Palestine.

Study Objectives

- Primary: To evaluate the effectiveness of the intervention on CPITN and S-OHI scores.
- Secondary: To assess changes in oral hygiene practices, dietary habits, and smoking behaviours.

Data Preparation and Management

Data were entered into IBM SPSS Statistics version 25.0.

All data were reviewed for completeness and consistency prior to analysis.

Normality testing was conducted using Shapiro-Wilk tests.

Missing data was minimal and handled by complete case analysis.

Statistical Analyses

Descriptive statistics will be used to summarise baseline characteristics by group (mean \pm SD, frequencies, percentages).

- Paired t-tests will be used to assess within-group differences from baseline to post-intervention.
- Independent t-tests were used to compare mean differences between the intervention and control groups.
- Statistical significance was set at $p < 0.05$.
- Confidence intervals were calculated at the 95% level for all primary outcomes.

Study Questions VS Analysis Plan

1. Can interactive educational sessions reduce **Community Periodontal Diseases Index** scores among 9th-grade students in Nablus City for two months?

1. Data Type and Variables

Dependent Variable: Community Periodontal Index for Treatment Needs (CPITN) **score** → Continuous quantitative variable

Independent Variable: Group type (Intervention vs. Control) → Binary categorical variable

Time Points: Pre-intervention (baseline)

Post-intervention (after two months) → true experimental design (pre-post measurements)

2. Statistical Design

Since there are two time points and two groups, the analysis includes:

A. Within-Group Analysis (Intervention group and control group):

Purpose: To assess whether there is a significant reduction in CPITN scores after the interactive educational sessions within the two groups themselves.

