Test to use: Paired t-test, as the data is normally distributed.

B. Between-Group Analysis (Post-intervention comparison):

Purpose: To compare the post-intervention CPITN scores between the intervention and control groups.

Test to use: Independent T-test as the data is normally distributed

Note: The two groups were examined for their differences in baseline measurement.

2. Can interactive educational sessions reduce **S-Oral hygiene index scores** among 9th-grade students in Nablus City within two months?

1. Data Type and Variables

Dependent Variable: Simplified Oral Hygiene Index (S-OHI) score → Continuous quantitative variable

Independent Variable: Group type (Intervention vs. Control) → Binary categorical variable

Time Points: Pre-intervention (baseline)

Post-intervention (after two months) → true experimental design

2. Statistical Design

Since there are two time points and two groups, the analysis includes:

A. Within-Group Analysis (Intervention group only):

Purpose: To assess whether there is a significant improvement (reduction) in S-OHI scores after the interactive educational sessions.

Test to use: *Paired t-test*, as the data is normally distributed.

B. Between-Group Analysis (Post-intervention comparison):

Purpose: To compare the post-intervention S-OHI scores between the intervention and control groups.

Test to use: *Independent t-test*, as the data is normally distributed

3. Will oral hygiene practices, smoking habits, and dietary habits improve among 9th-grade students after interactive educational sessions are applied in Nablus City?

Questionnaire responses related to oral hygiene practices, dietary habits, and smoking behaviour were **recoded** into scale variables to facilitate the computation of mean scores pre-and post-intervention. Correct answers reflecting preventive behaviours, in line with American Dental Association (2023) guidelines, were assigned the highest scores, while incorrect responses received the lowest scores, for example:

- "Do you clean your teeth?": Yes = 1, No = 0
- "How often do you clean your teeth?": Once/day = 1, Twice/day = 2, Three times/day = 3
- "How long does it take to clean your teeth?": One minute = 1, Two minutes = 2, More than two minutes = 3, Don't know = 0
- "Brushing technique": Scrubbing = 1, Bass = 2, Modified Bass = 3
- "Toothbrush type": Hard bristle = 1, Soft bristle = 2, Medium bristle = 3

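### The stated G*Power inputs give 44 pairs, not the 536 and 410 students called required, and the between-arm test has no sample-size basis

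*Protocol*

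**What the plan says.** The sample size is set out in the Protocol under Sample techniques and process, in the text after Table 1. Two programs are named there.

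- **Epi Info.** "The Epi Info program was used to calculate the sample size based on schools with 9th-grade classes", followed by the counts of eligible schools by area (27, 25 and 13) and the selection of 15 schools.
- **G*Power.** This was used for students, with effect size dz = 0.5 and an alpha "of 0.05 and a study power of 90"%. The paragraph attributes the result to these calculations: "536 students from intervention schools and 410 students from control schools were required to obtain accurate and meaningful data".

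The test, its sidedness and the reason for unequal arms are not given. The SAP has no sample-size section. It plans paired t-tests within groups. Between arms, its Statistical Analyses list says "Independent t-tests were used to compare mean differences between the intervention and control groups", while the plan for Question 1, part B, reads "Purpose: To compare the post-intervention CPITN scores between the intervention and control groups". The significance rule is "Statistical significance was set at $p < 0.05", with no mention of one or two sides.

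On allocation, the sample-size paragraph speaks of intervention schools and control schools. Under Data Collection Processes the Protocol says "The selected participants were randomly divided into intervention and control groups".

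**The concern.** A sample-size statement should let a reader go from the inputs to the number. Here the inputs are conventional and the number is roughly ten times what they imply.

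The effect index also belongs to a different test. dz is the mean within-student change divided by the SD of that change, so it sizes the before-after test in a single group. Whether the programme works compared with the control session is answered by the independent t-test between arms. That test needs a between-arm effect size, and neither document gives one.

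A reader therefore cannot tell what between-arm difference the trial was sized to detect, or whether the 90% applies to it. The fault lies in the power statement and does not bias the estimates.

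**Working it through.** **Inputs from the Protocol.** dz = 0.5; alpha 0.05; power 0.90; stated requirement 536 + 410 = 946 (ratio 536/410 = 1.307); 15 schools. Sidedness is not stated, so two-sided is assumed and one-sided is shown where it matters.

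**1. Attempt to reproduce the stated figure (paired t-test).** Power is P(T > t_crit), where T is noncentral t with n − 1 df and noncentrality 0.5·√n.

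| Test | n | Power |
|---|---|---|
| Two-sided | 43 | 0.893 |
| Two-sided | 44 | 0.900 |
| One-sided | 35 | 0.895 |
| One-sided | 36 | 0.903 |

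The stated inputs require 44 pairs (36 one-sided). The stated totals are 536/44 = 12.2 and 410/44 = 9.3 times that. Working backwards, 536 and 410 pairs have 90% power at dz of about 0.14 and 0.16, not 0.5.

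**2. Most generous reading: 0.5 as a between-group d.** The noncentrality is 0.5/√(1/n₁ + 1/n₂), with n₁ + n₂ − 2 df, two-sided.

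| n₁/n₂ | Power |
|---|---|
| 85/85 | 0.8999 |
| 86/86 | 0.9032 |
| 98/75 | 0.8999 |
| 99/75 | 0.9011 |

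This gives 86 per arm, or 99 and 75 near the stated ratio. Alpha of 0.01 (63 pairs or 121 per arm) or 0.001 (90 pairs or 170 per arm) does not reach the stated totals either.

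**3. Could an unstated design effect bridge the gap?** From 99/75 it would have to be 536/99 = 5.41 and 410/75 = 5.47. With m = 946/15 = 63.07 students per school, a design effect of 5.4 implies ICC = 4.4/62.07, about 0.07. With 15 schools in two arms (13 df), power at 0.5 SD would then be about 0.86, so this route does not recover 90% either. The ICCs in the Protocol (0.83 and 0.98, under Clinical Screening) measure examiner agreement, not similarity of students within schools.

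**4. What 536 and 410 detect between arms with 90% power.** The basic standard error, in SD units, is √(1/536 + 1/410) = 0.0656.

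- *Students independent:* (1.960 + 1.282) × 0.0656 = 0.213 SD. Power at 0.5 SD exceeds 0.999.
- *Whole schools allocated:* the standard error is multiplied by √DE, with DE = 1 + (m − 1)·ICC and noncentral t on 13 df. The ICCs and equal school sizes are assumptions.

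| Assumed ICC | DE | Detectable at 90% | Power at 0.5 SD |
|---|---|---|---|
| 0.01 | 1.62 | 0.29 SD | >0.999 |
| 0.05 | 4.10 | 0.47 SD | 0.935 |
| 0.10 | 7.21 | 0.62 SD | 0.747 |

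Power at 0.5 SD falls below 90% once the ICC exceeds about 0.060. If school sizes vary with an assumed CV of 0.5, DE = 1 + ((CV² + 1)m − 1)·ICC. The threshold then drops to about 0.048, and power at ICC 0.05 is 0.889.

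**5. Which SD.** These effects are in SDs of the outcome compared, and the SAP names both change and post-intervention scores. With equal variances, change SD = post SD × √(2(1 − ρ)). So 0.213 change-score SDs equal 0.25, 0.21 and 0.16 post-score SDs at assumed pre-post correlations of 0.3, 0.5 and 0.7.

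**The case against.** The strongest reply is that the error runs in the safe direction. The sample is far larger than the inputs require, power at 0.5 SD exceeds 99.9% if students are independent, and the promised 95% confidence intervals will show the precision whatever the planning text says. That stands if students were allocated individually and behave independently. It does not stand if schools were allocated: power then depends on an ICC that the documents do not give, and unadjusted intervals would be too narrow.

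A second reply is that the derivation may be incomplete rather than wrong. Two programs and published guidance are mentioned, so an unstated input may have produced the totals. This is fair, and the claim is limited accordingly: the inputs as stated do not give the totals, and no step that would is shown. The Epi Info sentence lists only school counts and appears to concern the number of schools.

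Third, the SAP names neither the paired nor the independent test as primary, so dz does match one planned analysis. That is correct. But the SAP makes group its independent variable and the aim is effectiveness, and for the between-arm test there is no sizing at all.

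Finally, the school-level figures rest on assumed ICCs and on 13 df. With a normal reference distribution they would be 0.27, 0.43 and 0.57 SD. With so few schools 13 df is the more suitable choice, and the conclusion is the same either way.

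**Conclusion.** The concern holds. The sample-size statement is wrong as written, because dz = 0.5, alpha 0.05 and 90% power call for 44 pairs two-sided (36 one-sided) and no reading tried of the stated inputs gives 536 and 410. The stated 90% does not carry over to the between-arm comparison, for which no effect size or power is given.

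This does not show that the trial is underpowered. With independent students the sample is ample for 0.5 SD. With school allocation, 90% power at that effect is not assured. The answer turns on an ICC near 0.05 to 0.06, under the assumptions of 15 schools, 13 df and a school-size CV between 0 and 0.5. The point should be fixed, and the shortfall is in the planning statement rather than in the results.

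**What to change.** Rewrite the sample-size paragraph as follows.

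1. Give the inputs that actually produced 536 and 410 (test, sidedness, effect size, allocation ratio, ICC or design effect, attrition). If they cannot be recovered, withdraw the claim that the totals follow from dz = 0.5, describe them as the numbers included if that is what they are, and report that the stated inputs need 44 pairs two-sided (36 one-sided).
2. Say what the Epi Info calculation covered.
3. Reconcile the Protocol's sample-size paragraph with Data Collection Processes on whether schools or students were allocated. Reconcile the SAP's Statistical Analyses list with its Question 1 plan on whether change or post-intervention scores are compared.
4. State the between-arm effect detectable with 90% power at 536 and 410, in SDs of the outcome actually compared: about 0.21 SD if students are independent. If schools were allocated, give a range over stated ICCs with the df and school sizes used, and say that 90% power at 0.5 SD is not assured. Label it as calculated after the sample was fixed.

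The cost is one paragraph and no extra students. The drawback is that the restated power may look less favourable, and under school allocation it stays uncertain until an ICC is given.

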### **Clinical Screening**

In this study, the Community Periodontal Index for Treatment Needs (CPITN) was used to assess the prevalence of periodontal disease (PD) among 9th-grade students before and after the intervention. For adolescents, CPITN scores 0, 1, and 2 are used to assess gingivitis:

- Score 0: Healthy gingiva
- Score 1: Gingival bleeding observed after gentle probing
- Score 2: Presence of supra or sub-gingival calculus

For adults, CPITN includes the following scores for periodontitis:

- Score 3: Pathological pockets measuring 4 to 5.99 mm deep

Score 4: Pathological pockets measuring 6 mm or deeper

Each sextant of the mouth examined was assigned a code number, with the index teeth representing each sextant: 16, 11, 26, 36, 31, and 46 (22).

The Oral Hygiene Index-Simplified (OHI-S) was used to determine the oral hygiene status of the subjects. This index consists of two components: debris and calculus, each with a possible score range of 0 to 3. The amounts of calculus and debris were assessed by examining the facial surfaces of teeth numbers 11, 16, 26, and 31 and the lingual surfaces of teeth 36 and 46. The scores for calculus and debris were added together and divided by the number of examined surfaces to calculate the OHI-S score for each individual.

In the pilot phase of the study, the Interclass Correlation Coefficient (ICC) was calculated to assess the reliability of the clinical measurements. A total of 20 students were examined five times by five data collectors, resulting in ICC values of 0.83 for CPITN and 0.98 for OHI-S, indicating high reliability.

### **Instrument Development**

The questionnaire utilised in this study was adapted from existing literature with modifications to align with the study's primary objective. The secondary aim was to evaluate the impact of the interactive oral education program on students' oral hygiene practices, dietary habits, and smoking behaviours two months after the implementation of the educational sessions. Initially, the questionnaire was developed in English and later translated into Arabic. To ensure accuracy, the translation was validated through a back-translation process from Arabic to English before being administered as a pre-test.

The questionnaire consisted of pretested standardised closed-ended questions that were assessed for face and content validity by three experts in the field. It was divided into five sections:

1. **Student Background:** This section included questions about the type of school (governmental or private) and the school system.
2. **Family Background:** The questions covered family size, parents' educational and occupational status, and the family's economic status.
3. **Oral Hygiene Practices:** This section addresses the frequency and technique of tooth brushing.
4. **Dietary Habits:** Questions focused on the frequency of breakfast consumption per week and the daily intake of nutritious versus non-nutritious foods.
5. **Smoking Behaviours:** This section assessed the frequency of cigarette and water pipe smoking and the number of cigarettes consumed.

The questionnaire's internal consistency was also evaluated using Cronbach's alpha, yielding a reliability coefficient of 0.967 for the 47 items tested.

The questionnaire was administered through direct interviews with individual students. All participants completed the questionnaire and underwent clinical examinations, resulting in

a 100% response rate. The questions in the questionnaire were designed to align with the topics covered in the educational program.

### **Data Collection Processes**

The Al-Quds Committee for Ethical Considerations approved this study (REF.13/24). Consent forms were distributed to students, and their approval was sought before data collection began.

The researcher trained five dentists to conduct interviews and dental examinations, ensuring the data collection process was standardised and calibrated. Training sessions for the data collectors were held every 15 days throughout the research period to maintain consistency and accuracy in data collection.

During the baseline phase, all participants were provided with a comprehensive explanation of the study. Baseline data were collected in March 2024. The selected participants were randomly divided into intervention and control groups, ensuring that both groups were matched by age and gender. The control group received one oral educational session, while the intervention group participated in six sessions. The educational sessions were held every 10 days over two months.

After two months of interactive education, participants were re-examined and interviewed. Follow-up data were collected in the same schools using the same dental examination measures and questionnaires used during the baseline phase.

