**Table (2): Educational Sessions Program**

Session No.	Session Title	Duration & Group Size	Learning Objectives & Content	Teaching Methods	Instructional Tools	Evaluation Strategy
1	Anatomy & Physiology of the Oral Cavity and Clinical Presentation of Periodontal Disease	45–60 minutes, 30–35 participants	Objectives: Identify the major anatomical structures of the oral cavity; Explain the normal function of periodontal tissues Content: Overview of teeth, gingiva, periodontal ligament, alveolar bone; Signs and clinical presentation of periodontal disease (PD)	Interactive lecture & Q&A	Smartboard, photographs, PowerPoint, dental models	Prepare a brief report on a family member's oral condition
2	Prevention and Treatment of Periodontal Disease	45–60 minutes, 30–35 participants	Objectives: Describe primary preventive measures against PD; Compare non-surgical treatment options	Group discussion & live demonstration	Whiteboard & markers, photographs, PowerPoint	Compile a list of barriers to effective oral hygiene

			Content: Oral hygiene techniques: brushing, flossing, mouthwash; Professional measures: scaling, polishing, fluoride application		
3	Maintenance and Follow-Up of Preventive Measures	45–60 minutes, 30–35 participants	Objectives: Outline a maintenance schedule for periodontal health; Apply problem-solving strategies to common barriers  Content: Recall intervals and re-evaluation protocols; Strategies for overcoming patient-identified maintenance barriers	Brainstorming & group discussion	Photos, preventive devices (toothbrush, floss, mouthwash), posters, puzzles
4	Daily Preventive Practices	45–60 minutes, 30–35 participants	Objectives: Practice correct brushing and interproximal cleaning techniques;	Live demonstration under supervision	Whiteboard, PowerPoint, tooth models, preventive

			Reinforce daily oral-care routines	& mini-lecture	devices (brush, floss, mouthwash)
			Content: Live demonstrations of toothbrush and floss use; Hands-on practice with models and peer feedback		
5	Smoking and Its Harmful Effects on Periodontal Tissues	45–60 minutes, 30–35 participants	Objectives: Explain how tobacco smoking damages periodontal tissues; List short- and long-term oral health effects of smoking	Live demonstration on under supervision & lecture	Colorful PowerPoint slides with photos
			Content: Chemical effects of nicotine and tar; Epidemiology of PD in smokers vs. non-smokers		Compile a resource list on the oral-health impacts of smoking

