"Toothbrush replacement frequency": Every three months = 1, Two months = 2, Monthly = 3

Additional coding schemes are provided at the end of this document. The overall mean differences in oral hygiene practices, dietary habits, and smoking behaviour scores were then compared between groups using independent sample t-tests, with sub-analyses conducted for each behavioural domain separately. Statistical significance was set at $p < 0.05$.

1. Data Type and Variables

Dependent Variables (Behavioural Scores):

- **Oral hygiene practices score** → Continuous quantitative
- **Smoking habits score** → Continuous quantitative
- **Dietary habits score** → Continuous quantitative

Independent Variable: Group type (Intervention vs. Control) → Binary categorical

Time Points: Pre-intervention (baseline)

Post-intervention (after two months) → True experiment design (pre-post)

2. Statistical Design

Since the question involves **multiple behaviours** and **two time points**, the analysis will be conducted separately for each behavioural domain:

A. Within-Group Analysis (Intervention Group Only)

- **Purpose:** To evaluate if there was a significant improvement in each behaviour **after the intervention**.
- **Test to use:** Paired t-test for:
 - Oral hygiene practices score

- Dietary habits score
- Smoking habits score

(Assumes normal distribution)

B. Between-Group Analysis (Post-Intervention Comparison)

- **Purpose:** To compare post-intervention behavioural scores between intervention and control groups.
- **Test to use:**
 - **Independent t-test** for:
 - Oral hygiene practices
 - Dietary habits
 - Smoking behavior

(Assumes normal distribution)

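### The between-arm t-tests ignore gender, the baseline score and the unit of allocation, so the 95% intervals do not reflect how the arms were formed

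*Protocol*

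**What the plan says.** **How the arms were formed.** Protocol, Data Collection Processes: "The selected participants were randomly divided into intervention and control groups", and the same sentence goes on "ensuring that both groups were matched by age and gender". No strata, pairing or procedure is given.

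**Unit of allocation.** The sentence above divides participants. The sample-size text under Table 1 points to whole schools: "536 students from intervention schools and 410 students from control schools were required to obtain accurate and meaningful data". The same section says "A total of 15 schools were selected".

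**Between-arm tests.** The SAP's general list (Statistical Analyses) compares mean differences between arms by independent t-test. For CPITN, Study question 1 B compares post-intervention scores: "Independent T-test as the data is normally distributed". Study question 2 B does the same for S-OHI. For the behaviour scores, Study question 3 has mean differences "compared between groups using independent sample t-tests", and its part B compares post-intervention scores. A note under question 1 says that the groups were checked for baseline differences, but no adjustment follows from it. The primary outcomes are to have 95% intervals.

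**The concern.** A confidence interval is right only if its standard error matches the way the arms were formed. Two features of the formation matter here, and they pull in opposite directions.

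- Balancing the arms on a prognostic factor takes that factor out of the true variance of the arm difference. An unadjusted t-test leaves it in the error term, so on this count alone the interval is too wide.
- Allocating whole schools makes students within an arm correlated. A student-level t-test treats them as independent, so on this count the interval is too narrow.

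The SAP accounts for neither. At stake is whether the stated 95% means 95% for CPITN and S-OHI, and whether p < 0.05 keeps its nominal error rate. Random division alone also cannot guarantee matching, so any gender imbalance that is left stays in the unadjusted estimate.

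**Working it through.** **Inputs from the documents.** Arms of 536 and 410 (total 946) and 15 schools, so m = 946/15 = 63.07 students per school. All students are in 9th grade and are described as 15 years old (Primary Aim).

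**Assumptions.** The documents give no outcome by gender, no SD and no between-school correlation. I take gender to explain R² = 1 to 10% of the variance, and the between-school correlation ρ to be 0.01 to 0.05. The coefficients of 0.83 and 0.98 under Clinical Screening measure examiner reliability and cannot stand in for ρ.

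**1. The plan's own figure.** The plan states no standard error or interval width. Its only related figure is the sample size, and it does not reproduce. With dz = 0.5, alpha 0.05 and 90% power, a paired t-test needs 44 students (36 one-sided). An independent t-test with an effect of 0.5 needs 86 per arm (70 one-sided). That is a separate matter; below, 536 and 410 serve only as arm sizes.

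**2. Planned interval.** Half-width = 1.96 × √(1/536 + 1/410) = 1.96 × 0.0656 = 0.1286 SD.

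**3. If students were allocated individually.** The adjusted half-width is 0.1286 × √(1 − R²). Coverage is that of the planned interval in 4,000 simulated trials per scenario with gender balanced in each arm. It was 95.2% at R² = 0.

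| R² | Adjusted half-width (SD) | Narrower by | Coverage of planned interval |
|---|---|---|---|
| 1% | 0.1279 | 0.5% | not simulated |
| 2% | 0.1273 | 1.0% | 95.6% |
| 5% | 0.1253 | 2.5% | 95.6% |
| 10% | 0.1220 | 5.1% | 96.5% |

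**4. If schools were allocated.** Design effect DE = 1 + (m − 1)ρ, and the correct half-width is 0.1286 × √DE. Coverage was simulated with 8 against 7 schools (an assumed split). The last column is 1 − 1/DE, the share of variance that age and gender would have to explain to bring the half-width back to 0.1286.

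| ρ | DE | Correct half-width (SD) | Wider by | Coverage of planned interval | R² needed to offset |
|---|---|---|---|---|---|
| 0.01 | 1.621 | 0.1637 | 27% | about 88% | 38% |
| 0.02 | 2.241 | 0.1925 | 50% | 81–82% | 55% |
| 0.05 | 4.103 | 0.2605 | 103% | about 67% | 76% |

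Coverage was practically the same with R² at 0, 5 or 10%. The table uses 1.96. With 15 schools and 13 degrees of freedom the multiplier is 2.16, so a valid interval is wider by a further 2.16/1.96 = 1.10.

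**5. Can gender balance across schools rescue the t-test?** Let g be the share of between-school variance that gender explains. With full credit for balance, the true standard error relative to the t-test's is √[(1 − ρ) + mρ(1 − g)].

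- ρ = 0.02, g = 0.5: √(0.98 + 63.07 × 0.02 × 0.5) = √1.611 = 1.27.
- ρ = 0.10, g = 0.1: √(0.90 + 63.07 × 0.10 × 0.9) = √6.576 = 2.56.

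The planned interval is too narrow even when gender explains half of the between-school variance.

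**6. Cost of adjustment at school level.** Without covariates: 15 − 2 = 13 degrees of freedom, t = 2.160. With three school-level covariates: 10 degrees of freedom, t = 2.228. The ratio is 1.031, about 3%.

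**The case against.** **The intervals are simply too wide.** A reader might infer from the matching that the unadjusted intervals are wider than the design allows. That follows only under individual allocation and only if gender is prognostic. Under school allocation the sign reverses (steps 4 and 5), and the documents do not settle which applies.

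**The excess width is 3 to 25%.** A reader might take this from √{[(1 − ρ) + mρ(1 − g)] / [1 + (m − 1)ρ]}, which runs from 0.971 (ρ = 0.02, g = 0.1) to 0.750 (ρ = 0.10, g = 0.5). But that ratio compares a school-level analysis with and without gender, and the SAP contains neither. It says nothing about the width of the planned t-test interval. Nor do the documents show that schools differ in gender mix; if they do not, g is near zero and so is the gain.

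**A slightly conservative interval is still valid.** This stands for individual allocation, where adjusting for gender is an efficiency choice worth a few percent.

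**The matching may be no more than a description.** This also stands in part. Arms of 536 and 410 rule out complete 1:1 pairs, so the statement can mean at most frequency balance, and no matched-pair analysis is called for.

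**Baseline may already be used.** If the mean differences in the SAP are change scores, baseline enters by subtraction. But the sections for each study question specify post-intervention scores, and neither version fits baseline as a covariate.

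**Conclusion.** The point holds in conditional form. No planned between-arm test has a term for gender, baseline score or school, so the intervals do not reflect how the arms were formed. The size and direction of the error turn on a fact that the Protocol gives in two conflicting versions.

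- **Students allocated:** intervals slightly too wide, by about 0.5 to 5% for R² of 1 to 10%. This rests almost wholly on gender, and it takes students' outcomes as independent. Sessions were delivered to groups ("45–60 minutes, 30–35 participants"), so some correlation could arise even here.
- **Schools allocated:** intervals too narrow, with coverage of about 88% at ρ = 0.01 and 67% at ρ = 0.05. No plausible gender effect makes up the difference.

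R², ρ and the 8-to-7 split of schools are assumptions. An unconditional claim that the intervals are too wide is not supported.

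**What to change.** 1. Reconcile Data Collection Processes with the sample-size text under Table 1, and state whether students or schools were allocated. Say there how balance on age and gender was achieved.
2. Replace the independent t-tests on CPITN, S-OHI and the behaviour scores with a model of the follow-up value on arm, baseline value and gender. Age is optional. If schools were allocated, add a school effect with small-sample degrees of freedom, or analyse at school level. Take the 95% intervals from this model.
3. Confirm that age and gender are on file for every student. The matching implies it, but the questionnaire sections listed under Instrument Development name neither.

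**Cost.** SAP wording and a few degrees of freedom. With individual allocation and 946 students the loss is negligible. With 15 schools and three school-level covariates the critical value rises from 2.16 to 2.23, about 3%, which could cancel the gain from gender at its low end. If the t-tests have already been run, the model should be reported as a labelled re-analysis.
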